#### B.1. Understanding individual patient differences in treatment response

A critical, but often understudied, issue in rehabilitation is predicting individual patient differences in treatment response. As reviewed in section A.1, a wide range of therapies exist for the treatment of hemiparesis, and several recent RCTs comparing two active treatments have reported equivalent benefits at the group level [9, 30, 31]. It would be clinically valuable to understand the characteristics of patients who do and do not respond to each therapy given the magnitude of these individual differences. For example, in a recent RCT of MT for chronic stroke patients [20], improvement in the Brunnstrom scale outcome measure ranged from 0% to 33% (estimated from two standard deviation above and below the mean of 16.5% improvement). Information about predicted individual differences would be useful for clinicians when deciding the course of treatment most likely to benefit the patient.

We assert that individual differences in response to MT are predictable through an understanding of the mechanisms responsible for MT's therapeutic benefit. The assembled team composed of researchers trained in the basic science of sensorimotor control ([name]) and its application to stroke patients (Drs. [name], [name], and [name]) is uniquely positioned to address this issue. The project is innovative because it will test competing predictions regarding the mechanism of MT by utilizing individual differences in lesion location and the integrity of four sensorimotor processes that may underlie MT's benefit. As an overview, we will first discuss the four sensorimotor processes that may underlie the mechanisms of MT's benefit (B.2), and then proceed to a summary of the

Albert Einstein Healthcare Network <hr/> Einstein	AEHN Protocol/Summary		
	NUMBER	DATE	PAGE
	HRP-204	11/1/2011	4 of 27

neural substrates that subserve these processes (B.3). Following this will be a discussion of the behavioral tasks we will use as convergent validity tests of the neuroanatomic predictions (B.4). Finally, we will summarize all of these predictions in Table 1.

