### B. 4. Converging evidence between lesion location and other behavioral tests

In addition to making predictions about the integrity of the four processes that may underlie MT's benefit based on lesion location, we will measure performance on confirmatory behavioral tests to (1) provide further evidence about the neural substrates of these functions and (2) allow clinicians to have simple behavioral tests to predict individual differences in MT response without having to rely on lesion location information. All behavioral tests have been previously used in our labs. For action observation, we will use a test that involves viewing sequentially presented video pairs of actions, with the patient making same/different judgments about the actions [68]. For proprioceptive feedback, we will use the RASP [69], a standard clinical measure of proprioception that will also be a primary outcome measure. For visual-proprioceptive feedback, we will use a visual-analogue scale of initial mirror illusion sensation (rate how strongly it feels as if the arm you see in the mirror is actually the arm behind the mirror) and a simple judgment task (Parson's task [70]) that has been shown to require integration of visual and proprioceptive input. In this task, patients judge whether a visually presented hand is a left or right hand. These judgments are affected by the orientation of the participant's own hand, suggesting the decision is based on the seen and felt position of the body. We will have patients make verbal judgments while we systematically manipulate the orientation of the patients' hand. Finally, motor imagery will be assessed using consistency

Albert Einstein Healthcare Network Einstein	AEHN Protocol/Summary		
	NUMBER	DATE	PAGE
	HRP-204	11/1/2011	6 of 27

on a grasping imagery task [71] in which patients report how they imagine they would grasp a handle (overhand or underhand) and compare the imagined results to their actual grasping of an object. Table 1 summarizes the preceding three sections.

PROCESS	NEURAL SUBSTRATE	CONFIRMATORY BEHAVIORAL TEST
Action observation	IFG, IPL, pMTG	Spatial action recognition task
Proprioceptive feedback	SI, SII	RASP
Visual-proprioceptive integration	IPL, BA5	Parson's task, screening questionnaire
Motor imagery	IPL, BG, PM	Imagined grasping

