##### b. For prospective studies:

i.) Total number of subjects planned to be enrolled in the study at AEHN site(s): 140 screened in single session, with target of 100 meeting inclusion criteria for the full treatment study

ii) For multi-site projects, please indicate total number of subjects planned to be enrolled in the study at all sites: Of the 100 participants that will meet inclusion criteria for the full treatment study, approximately 60 will be recruited to the brain imaging (including both MRI and CT) study conducted at U. Penn. The rest will have already received brain scans through their

Albert Einstein Healthcare Network Einstein	AEHN Protocol/Summary		
	NUMBER	DATE	PAGE
	HRP-204	11/1/2011	7 of 27

participation in MMRI sponsored studies included the Moss Research Registry and conducted via the "Cognition and Action" or "Language and Aphasia" laboratories.

iii) Describe access to a population that would allow recruitment of the targeted number of subjects (*i.e. how many potential subjects do you have access to? What percentage of those potential subjects do you need to recruit?*) : Patients and controls will be recruited from the Moss Research Registry; the requisite approval has been obtained from Registry Coordinator. The registry contains medical records of patients who have already agreed to participate in studies, allowing us to pre-select patients based on the likelihood of meeting inclusion criteria. Patients will also be recruited using a flyer distributed by therapists in the clinical programs at MossRehab and by the research staff to participants in stroke support groups in the Philadelphia metropolitan area.

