#### C.7. THERAPY REGIMEN

**a. Group assignment:** A research assistant (RA), who will not be involved in any assessments, will assign patients to the MT or placebo therapy (identical therapy with an opaque divider rather than a mirror) using stratified randomization based on the patient's Fugl-Meyer score. Before starting the trial an assignment order will be developed based on whether a patient's pre-treatment Fugl-Meyer score was low (between 10 and 30) or moderate (between 30 and 50). A previous MT RCT using a similarly chronic patient population and an identical placebo therapy showed little benefit of the placebo therapy. Thus, we must consider a balance between the scientific requirements of an appropriate control group and the ethical considerations of using patients' time to complete a therapy that is known to be ineffective. To balance these considerations, we will assign patients to the MT and placebo treatment groups in a 2:1 ratio, respectively. This inequality in sample size will only reduce statistical power by approximately 3% [81]. In addition, patients assigned to placebo treatment will be given the option of being crossed over to receive MT after the three month assessment. Patients will not be aware of which therapy is the placebo because both therapies will be described as studying the role of visual feedback rather than a test of "mirror therapy." Both treatments will include 2 daily 30 minute

Albert Einstein Healthcare Network <hr/> Einstein	AEHN Protocol/Summary		
	NUMBER	DATE	PAGE
	HRP-204	11/1/2011	12 of 27

therapy sessions, 5 days per week over a 4 week period.

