**C.13. Testing Specific Aim 3 (predicting individual differences in therapeutic benefit)**

All tests of Specific Aim 3 will focus on data from the MT group only.

a. Testing predicted relationships between processes underlying MT and MT benefit using lesion location: We will examine the relationship between the change in primary and secondary outcome measures and lesion location using whole-brain voxel-based lesion-symptom mapping (VLSM) analyses [83]. VLSM measures whether a behavioral score systematically differs between participants with and without damage to each voxel under investigation. Tests of this difference use a t-statistic to describe the difference in means between the damaged-group and non-damaged-group while taking into account the variances within each group. The t-statistic is thus used as a convenient measure of group differences, without the intention of comparing it to the parametric t distribution. Instead, statistical significance will be determined by non-parametric permutation tests [84], in which the distribution used for inferential statistic calculations are created by sampling from the observed data rather than assuming an a priori distribution. Thresholds for significance will be calculated from the 95th percentile of this distribution, to ensure a family-wise false positive rate of 0.05 [84]. The total number of comparisons will also be reduced by only performing analyses on those voxels that are damaged in at least 10% of participants (to avoid undue influence of a small number of participants).

As in the previous measures, we will use an ANCOVA-like procedure to determine whether post-treatment scores (the DV) are affected by damage status to each individual voxel under consideration (the IV) after controlling for pre-treatment score and total lesion volume (covariates). Separate VLSM analyses will be done for each primary and secondary outcome

Albert Einstein Healthcare Network Einstein	AEHN Protocol/Summary		
	NUMBER	DATE	PAGE
	HRP-204	11/1/2011	16 of 27

measure. The voxels identified as being predictive of MT benefit using the VLSM analysis should be consistent with the a priori ROI predictions (Table 1). VLSM will also allow us to test whether voxels outside of these ROIs predict MT benefit.

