- b. Testing predicted relationships between processes underlying MT and MT benefit using behavioral scores: In addition to using VLSM to test how the proposed neural substrates of the four sensorimotor processes are able to predict MT's benefit, we will also use the confirmatory behavioral measures (our proxy for the integrity of the processes) to predict MT's benefit. We will use linear stepwise regression to predict post-treatment scores (the DV) using each behavioral measure (the second level predictor/ IV) after controlling for pre-treatment score (the first level predictor/ IV). Note that this analysis is identical to the ANCOVAs used above except that a continuous IV is used, thus requiring regression rather than ANOVA. Analyses will be done separately for each of the four processes and each primary and secondary outcome measure. Testing our predictions about the processes will involve examining the sign and significance of second level predictor's regression weight. For example, if poor proprioception leads to reduced benefit of MT (see B.2), the regression weight for RASP (where high score corresponds to better proprioception) will be significantly positive. Alternatively, if poor proprioception lead to increased benefit of MT, the regression weight will be significantly negative. Finally, if proprioception does not affect MT benefit, the regression weight will not significantly differ from zero. Determining the influence of action observation, visual-proprioception integration, and motor imagery will use the same logic.
- c. Testing predicted relationships between lesion areas and confirmatory behavioral measures  
As summarized in Table 1, we predict that damage to particular ROIs will cause deficits in particular sensorimotor processes, which we will assess using the confirmatory behavioral tests. We will test these predictions in two ways. First, we will use t-tests to determine whether the pre-treatment confirmatory behavioral tests (the only time the tests are administered) will differ as a function of damage status to a particular ROI (using a 20% of volume criteria). Second, we will use linear stepwise regression to predict behavioral measure scores using percent damage to each predicted ROI after first controlling for total lesion volume. We have previously used both approaches successfully in a study of action observation [68].

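### B.4 wants the behavioural tests to predict individual MT response, but C.13.b specifies only sign and significance and plans no measure of predictive accuracy

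*Combined protocol and SAP*

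**What the plan says.** B.4 lists two reasons for the behavioural tests. The first concerns neural substrates. The second is to "allow clinicians to have simple behavioral tests to predict individual differences in MT response without having to rely on lesion location information". B.1, in the background, gives the motive: "Information about predicted individual differences would be useful for clinicians when deciding the course of treatment most likely to benefit the patient".

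The analysis is in section 6.g.ii, C.13.b: "We will use linear stepwise regression to predict post-treatment scores (the DV) using each behavioral measure (the second level predictor/ IV) after controlling for pre-treatment", where the last word refers to the baseline value of the same outcome. The criterion follows: "Testing our predictions about the processes will involve examining the sign and significance of second level predictor's regression weight". Either sign is of interest, as the proprioception example shows: "Alternatively, if poor proprioception lead to increased benefit of MT, the regression weight will be significantly negative". The regressions are run separately for each of the four processes and each primary and secondary outcome. The analysis set is one arm: "All tests of Specific Aim 3 will focus on data from the MT group only".

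The documents plan no incremental R-squared, prediction error, prediction interval, cross-validation or validation sample for these tests. They also give no alpha for C.13.b and no power or effect size for Aim 3.

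**The concern.** A significant weight shows that a test is associated with the post-treatment score once the pre-treatment score is known. It does not show how much closer the prediction for a new patient comes to that patient's outcome. With several dozen patients the two can differ widely: a weight can be clearly non-zero while individual predictions hardly move.

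The plan accepts this distinction elsewhere. In C.12 it declines inferential tests for dosing, partly because a large sample could make differences of doubtful clinical importance significant. C.13.b does not apply the same caution, although B.4 states a clinical use just as openly.

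At stake is what the trial can say about its second B.4 purpose. Analysed only as C.13.b describes, it could report significant predictors without showing whether they improve on the pre-treatment score by a useful amount.

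**Working it through.** The plan gives no figure for Aim 3 that could be reproduced, so the check starts from the design.

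**Inputs**
- Total sample, section 5.b: "140 screened in single session, with target of 100 meeting inclusion criteria for the full treatment study".
- Allocation, C.7.a: "we will assign patients to the MT and placebo treatment groups in a 2:1 ratio, respectively". The MT arm is 100 × 2/3 = 66.7, about 67.
- Model, C.13.b: intercept, pre-treatment score and one behavioural test. This is three parameters, so df = 67 − 3 = 64. C.13.b calls it stepwise, but the order of entry is fixed.
- Alpha: assumed 0.05, two-sided.
- Dropout: no rate is stated; assumed zero.

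**Smallest significant result**
- Critical t(0.975, 64) = 1.998.
- Partial r = t / √(t² + df) = 1.998 / √(3.99 + 64) = 0.242.
- Share of remaining variance explained: 0.242² = 0.059, or 5.9%.
- Cut in residual SD against the pre-treatment score alone: 1 − √(1 − 0.0587) = 0.030, or 3.0%. Adjusted for the extra parameter: 1 − √(0.9413 × 65/64) = 2.2%.
- Under bivariate normality, such a test puts 0.5 + arcsin(0.242)/π = 58% of patients on the correct side of the median residual, against 50% by chance.

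**Sensitivity to the assumptions** (cut in residual SD at the significance threshold)

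| n | Two-sided alpha | Cut |
|---|---|---|
| 67 | 0.10 | 2.1% |
| 67 | 0.05 | 3.0% |
| 67 | 0.05/4 | 4.8% |
| 67 | 0.05/32 | 7.6% |
| 60 | 0.05 | 3.3% |
| 54 | 0.05 | 3.7% |
| 33 | 0.05 | 6.3% |

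The row n = 33 illustrates the neglect outcome, which is measured only in right-hemisphere patients. Their share is not stated; about half of the arm is assumed.

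**Stronger predictors.** By the Fisher z approximation, the true partial r with 80% power at n = 67 is tanh[(1.960 + 0.842)/√63] = 0.34, a cut of 1 − √(1 − 0.115) = 5.9%. For 90% power, r = 0.39 and the cut is 7.8%.

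**Simulated leave-one-out gains** (n = 67, pre-treatment score plus one test, 4,000 data sets per value). The mean reduction in prediction error was 2.1% at a true partial r of 0.242 and 4.8% at 0.33.

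**Optimism after selection.** Four processes by eight outcomes (four primary, four secondary, section 6.d.i) give about 32 analyses, with no multiplicity control stated for C.13.b. If every test were null, 32 × 0.05 = 1.6 would be expected to be significant. In 20,000 simulated trials with a true partial r of 0.242, 51% were significant. Among those, the in-sample cut averaged 6.0% and the cut for new patients 2.2%. Leave-one-out does not remove this: a null predictor significant by chance still showed an apparent leave-one-out gain of 2.8%.

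**The case against.** The strongest reply is that the quoted criterion belongs to the process hypotheses. C.13.b asks whether intact proprioception, for example, helps, hinders or does not matter, and sign and significance answer that. This stands. The criterion is not wrong for its own question; the gap is that nothing further is specified for the second purpose in B.4.

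A reader might infer that a test with p < 0.05 would be handed to clinicians for choosing treatment. The documents do not say so. B.4 states a purpose, B.1 says such information would be useful, and no section contains a release rule or a treatment recommendation triggered by significance.

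A reader might also take 3% as the expected gain. It is the value exactly at the threshold, under an assumed alpha and no dropout, and a stronger predictor does better. A fitted regression would also normally yield an R-squared. That softens the point, but the plan neither commits to reporting it nor ties any statement about prediction to it.

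Finally, one could ask for a minimum gain, such as 10%, before any claim. The documents give no basis for a figure. A 10% cut needs a partial r of about 0.44, and even at that true value a leave-one-out estimate passes only about 42% of the time. A fixed bar is therefore not part of this point.

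**Conclusion.** The point holds as a gap between a stated purpose and the planned analysis. B.4 wants tests that predict individual response, and C.13.b supplies only a test of association. With two-sided alpha 0.05 and 67 patients analysed, a just-significant test cuts residual SD by about 3% and explains 5.9% of the remaining variance. Across the ranges shown for n, alpha and power, the cut stays at or below about 8%.

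The point does not reach the main efficacy comparison in C.11, data collection or patient care. It is a worthwhile improvement to a third aim.

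One limit remains whatever accuracy is found. Aim 3 uses the MT arm only, so its results can show prediction of outcome under MT. They cannot show who gains more from MT than from another therapy, which is the choice that B.1 has in mind.

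**What to change.** Keep sign and significance in C.13.b for the process hypotheses, and add for the prediction purpose in B.4:

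1. For each behavioural test and outcome, report the incremental R-squared over the pre-treatment score with its 95% CI.
2. Report the leave-one-out reduction in prediction error against the model with the pre-treatment score alone.
3. Base any statement about predicting individual response on these figures and not on p < 0.05.
4. State that leave-one-out does not remove the optimism from picking the best of about 32 analyses.
5. State that MT-arm results concern outcome under MT and do not show who would do better with MT than with another therapy.

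The cost is a few lines of analysis code and a short addition to the analysis plan; no visit, measurement or sample size changes. The downside is that some significant tests will be shown to add little.

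### C.13.c tests each region-to-process prediction with both an unadjusted t-test and a volume-adjusted regression and does not say which governs; the t-test can be significant from stroke size alone.

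*Combined protocol and SAP*

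**What the plan says.** Section 6.g.ii, C.13.c predicts that damage to the regions in Table 1 produces deficits in the matching sensorimotor processes. Of these predictions it says: "We will test these predictions in two ways".

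- First way: "we will use t-tests to determine whether the pre-treatment confirmatory behavioral tests" differ by damage status, where a region counts as damaged at 20% of its volume. No covariate is named.
- Second way: a stepwise linear regression of the behavioural score on "percent damage to each predicted ROI after first controlling for total lesion volume".

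C.13.a treats volume as the second way does: the voxel-based lesion mapping has pre-treatment score and total lesion volume as covariates. C.13.c does not rank its two analyses or say what follows if they disagree, and it states no significance level. C.13 opens with "All tests of Specific Aim 3 will focus on data from the MT group only", so the analysis set is the mirror therapy arm.

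**The concern.** Damage to a region is part of total lesion volume, so patients above a 20% cut will tend to have larger strokes. If larger strokes also depress test performance generally, the damaged group scores worse whether or not the region matters for the process. The t-test cannot separate the two explanations. The plan adjusts for volume in its other two lesion analyses and gives no reason for leaving it out here.

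At stake is the link from region to process. B.4 wants the behavioural tests to add evidence on neural substrates, and B.3 concedes that the Table 1 regions rest on incomplete and often conflicting findings. Table 1 lists the inferior parietal lobe for three of the four processes, so a group of large lesions reaching that region could seem to support three predictions together.

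**Working it through.** The plan gives no sample size, power or error rate for C.13.c, so there is no stated figure to reproduce. The check asks how often the t-test is significant when the region has no effect of its own.

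**Inputs from the documents**
- Section 5.b: 140 screened, "with target of 100 meeting inclusion criteria for the full treatment study".
- C.7.a: 2:1 allocation to mirror therapy and placebo. The mirror therapy arm is 100 × 2/3 ≈ 67, before dropout or missing scans.

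**Assumptions, not in the documents**
- 30% of patients are above the damage cut; two-sided 5% level.
- Lesion volume has correlation a with the propensity to have the region damaged, and correlation -b with the behavioural score.
- Given volume, region damage has no effect on the score. Volume acts linearly and is measured without error.

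**Closed-form approximation**
1. For a normal propensity, the cut leaving 30% above is 0.524, where the normal density is 0.348. Splitting there multiplies a correlation by 0.348/√(0.3 × 0.7) = 0.759.
2. The correlation of damage status with score, caused by volume alone, is q = 0.759 × a × b in size.
3. The t statistic is centred near d = √67 × q/√(1 − q²), with √67 = 8.19.
4. The false-positive rate is about P(Z > 1.96 − d) + P(Z < −1.96 − d).

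For a = 0.6 and b = 0.4: q = 0.759 × 0.24 = 0.182; d = 8.19 × 0.182/0.983 = 1.52; rate ≈ P(Z > 0.44) ≈ 0.33.

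**Results at n = 67.** The simulation column gives the spread over repeated runs of at least 2,000 replicates per setting, where more than one was made.

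| a, -b | q | d | Closed form | Simulated t-test |
|---|---|---|---|---|
| 0, 0 | 0 | 0 | 0.05 | 0.05 |
| 0.2, -0.2 | 0.030 | 0.25 | 0.06 | 0.06 |
| 0.3, -0.3 | 0.068 | 0.56 | 0.09 | 0.08 to 0.09 |
| 0.4, -0.3 | 0.091 | 0.75 | 0.12 | 0.11 to 0.12 |
| 0.6, -0.4 | 0.182 | 1.52 | 0.33 | 0.31 to 0.32 |
| 0.8, -0.5 | 0.303 | 2.61 | 0.74 | 0.71 to 0.73 |

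With volume in the model, the rate stays at 0.04 to 0.06 in every setting. This holds both for regression on the extent of damage and for the damaged/undamaged comparison with volume as covariate.

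**Disagreement.** At a = 0.5, b = 0.5, the t-test is significant and the adjusted regression is not in 30% of runs; at 0.7 and 0.5, in 57%. Under those assumptions the case on which the plan is silent would be common.

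**Fewer scans.** The shift d grows with √n. With 40 usable scans, as an illustration, the 0.6, -0.4 setting gives d = 6.32 × 0.182/0.983 = 1.17 and a rate of about 0.22.

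**Price of adjustment.** The variance inflation for damage status is 1/(1 − (0.759a)²): 1.10 at a = 0.4, 1.26 at 0.6 and 1.58 at 0.8. It is partly offset because volume also explains some of the variation in scores.

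**The case against.** The strongest reply is that the plan already contains the remedy. The sentence after the t-test sets out a volume-adjusted regression for the same predictions, using percent damage instead of a cut. A reader might infer from the t-test alone that C.13.c ignores lesion volume. Taken as a whole it does not, and a finding driven only by volume would be expected to fade in the second analysis.

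The plan also never says that one significant test is enough. B.4 speaks of converging evidence, and if both tests must be significant, with the adjusted slope in the predicted direction, the simulated false-positive rate is only about 1 to 3% in all these settings. That reading is possible but unstated. If either test may confirm a prediction, the error rate is at least that of the t-test. The objection narrows the point to a missing decision rule and an unadjusted test that should not stand alone; it does not remove it.

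It is also fair that the documents give no lesion-volume distribution and neither correlation, and do not establish that larger strokes lower every score. If either correlation is zero, the t-test keeps its 5% level. A reader might take the high rates in the table as the expected error of this study, but nothing in the documents supports choosing those rows over the weak ones. The team's statement that it has used both approaches before does not bear on the confounding.

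**Conclusion.** The point holds in limited form. C.13.c offers an unadjusted and a volume-adjusted test of the same predictions without saying which governs, and the unadjusted one can be significant through stroke size alone. With 67 patients and 30% damaged, its false-positive rate could lie anywhere from about 5% to about 71%, depending on correlations that the documents do not report. The adjusted test stays at about 5% provided the effect of volume is adequately captured by the covariate.

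A reader might go further and conclude that the trial's main results are at risk. They are not. C.11 compares the randomised arms and does not use lesion data, and the C.13.a mapping already adjusts for volume. Only the inference from region damage to pre-treatment process scores is affected. Nor does the plan claim that a region is necessary for a process; its prediction is that damage causes deficits. This is a cheap improvement, not a flaw in the efficacy analysis.

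**What to change.** Make two small changes to C.13.c.

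1. Replace the t-test with an ANCOVA of each confirmatory score on damage status (same 20% cut) with total lesion volume as covariate. Alternatively, keep the t-test and label it descriptive.
2. State that the conclusion on each Table 1 prediction rests on the volume-adjusted regression, whatever the group comparison shows.

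The second change alone closes the gap in the decision rule. The first brings the group comparison into line with the other lesion analyses.

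No new data are needed, since total lesion volume is already required for C.13.a and for the second C.13.c analysis. Adding the covariate costs one degree of freedom and some power, because region damage and total volume are correlated; the variance inflation above shows the scale.

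### C.13.c names stepwise regression over two or three regions per process and fixes the place of lesion volume only; it should specify forced entry with one block test

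*Combined protocol and SAP*

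**What the plan says.** Section 6.g.ii, C.13.c tests the lesion predictions in two ways. The first is a t-test for each region, comparing pre-treatment behavioral scores by damage status. The second is "linear stepwise regression to predict behavioral measure scores using percent damage to each predicted ROI", and it is done "after first controlling for total lesion volume". Table 1 (section B.4) lists three regions for action observation, two for proprioceptive feedback, two for visual-proprioceptive integration and three for motor imagery. The inferior parietal lobe appears under three of the four processes.

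C.13.c gives no entry or removal threshold, direction of selection, significance level, joint test or multiplicity rule. The one error rate in the analysis plan belongs to the voxel-based lesion mapping of C.13.a, where permutation thresholds are set "to ensure a family-wise false positive rate of 0.05".

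C.13.b, immediately before, uses the same term: "We will use linear stepwise regression to predict post-treatment scores (the DV) using each behavioral measure". There the order is explicit, "using each behavioral measure (the second level predictor/ IV) after controlling for pre-treatment score (the first level predictor/ IV"), and the plan adds that "this analysis is identical to the ANCOVAs used above except that a continuous IV is used".

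**The concern.** Stepwise regression is the usual name for a procedure in which p-values decide which predictors enter and stay. In C.13.b the name does no harm. There is one predictor of interest after the covariate, its level is stated, and the model is equated with ANCOVA. The plan also interprets a null there by saying that "if proprioception does not affect MT benefit, the regression weight will not significantly differ from zero", which presupposes that the weight is always estimated.

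C.13.c is different. Two or three regions follow the covariate, so there is something to select among, and no statement fixes their entry. An analyst who ran a software stepwise routine on the regions would be following the text.

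The quantity at stake is the evidence that a given region underlies a given process. Selection would report the best of two or three looks, overstate the weight of whatever entered, and sometimes credit a neighbouring region that tends to be damaged together with the true one. It would also leave no regression weight for predictions that failed. Because the inferior parietal lobe is predicted for three processes, its entry in one model and displacement in another could look like a dissociation when it is only a product of selection.

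**Working it through.** The plan states no error rate for C.13.c, so there is no figure to reproduce. The check asks what each reading of the text would give.

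**Inputs from the documents.** Two or three regions per process (Table 1). Lesion volume first (C.13.c). Analysis set: "All tests of Specific Aim 3 will focus on data from the MT group only", so with 100 patients allocated 2:1 (C.7.a), 100 × 2/3 ≈ 67.

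**Assumptions, not in the documents.** Two-sided entry at p<0.05. Pairwise correlation of 0 to 0.9 between regional damage percentages, given lesion volume. Correlation of 0.5 between each region and lesion volume.

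**Step 1, independent regions.** The chance that at least one of k null regions reaches p<0.05 is 1 − 0.95^k:
- k = 2: 1 − 0.9025 = 9.75%
- k = 3: 1 − 0.8574 = 14.3%

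With entry at p<0.10 instead, the values are 1 − 0.90² = 19% and 1 − 0.90³ = 27%.

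**Step 2, correlated regions.** Simulation under no regional effect, n = 67, lesion volume forced in, 8,000 runs per cell (simulation standard error near 5%: √(0.05 × 0.95/8000) ≈ 0.24 percentage points):

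| Correlation | 2 regions, any enters | 2 regions, block F | 3 regions, any enters | 3 regions, block F |
|---|---|---|---|---|
| 0 | 9.6% | 5.1% | 14.4% | 5.3% |
| 0.3 | 9.5% | 4.7% | 13.7% | 5.0% |
| 0.5 | 8.9% | 4.8% | 12.5% | 4.7% |
| 0.7 | 8.4% | 5.2% | 11.1% | 4.5% |
| 0.9 | 7.3% | 4.9% | 8.2% | 5.2% |

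At n = 100 the any-region rates for correlations 0 to 0.7 are 8.5-9.9% and 10.2-14.8%, so sample size matters little. A single pre-named region tested after lesion volume rejects in 4.6-5.3% of runs.

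**Step 3, where the excess comes from.** The event counted in Step 2 is that at least one region has p<0.05 when added alone to lesion volume. Separate unadjusted tests of each region after lesion volume give the same event, so the any-region rate measures multiplicity and is not peculiar to stepwise selection.

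**Step 4, what selection adds.** Suppose one region truly matters, with an assumed standardised effect of 0.35 in size, n = 67. Some region enters in about 80-83% of runs. Among those runs, the wrong region is picked first in:

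| Correlation | 2 regions | 3 regions |
|---|---|---|
| 0.3 | 3.9% | 6.7% |
| 0.5 | 6.6% | 11.1% |
| 0.7 | 12.5% | 21.3% |
| 0.9 | 25.7% | 38.1% |

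Running the full procedure with three regions (entry 0.05, removal 0.10, correlations 0.5-0.7), only a wrong region enters in roughly 7-16% of all runs at n = 67. When the true region is selected, its weight averages 0.38 to 0.44 in size, against a true 0.35. The ratios are 0.38/0.35 = 1.09 and 0.44/0.35 = 1.26, so the weight is roughly 10-25% too large.

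**The case against.** The strongest reply is that the plan supplies its own meaning of the term. C.13.b uses it for ordered entry, and C.13.c follows directly with the same construction: predict the score from the predictor after controlling for the covariate. Each predicted region may also mean one region per model, just as each behavioral measure does in C.13.b. On that reading nothing competes, nothing is dropped, and each test runs at about 5%. This stands as a plausible reading, and a reader who inferred that the plan has committed itself to automatic selection would be going beyond the text. It does not settle the matter, because the levels, the comparison with ANCOVA and the inference on a weight that resolve C.13.b are all absent from C.13.c.

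Second, 8-15% is what any two or three unadjusted tests give, and the region-by-region t-tests in the same section share it. This also stands. It limits what can be blamed on the word stepwise, but it leaves the process-level question without a joint or adjusted test on either reading.

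Third, the t-tests supply a group difference for every region whether or not it enters a regression. So what selection would remove is the weight adjusted for lesion volume, not all evidence on a failed prediction.

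Fourth, a reader might infer that correlated regions would be picked or dropped arbitrarily. The figures do not support that. At correlations of 0.3-0.7 the true region is picked first in about 79-96% of selections under the assumed effect. Chance plays a part, and a large one only when damage to the regions is very highly correlated.

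**Conclusion.** The point holds as a gap in specification with a definite consequence if the text is followed literally. Under automatic selection at an assumed p<0.05, a region would enter by chance in about 8-10% (two regions) or 10-15% (three regions) of null analyses per process at correlations of 0-0.7, falling to about 7-9% at 0.9. Of that excess, the multiplicity part arises with or without selection. The inflated weights, occasional credit to the wrong region and missing weights arise only with selection. The entry level, correlations and effect size are assumptions, because the documents give none of them.

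The documents do not establish that selection is intended, so these rates should not be quoted as the trial's error rates. In C.13.b only the name needs correcting. The issue is confined to a mechanistic check within Aim 3 that relates lesions to pre-treatment scores; the Aim 1 treatment comparison is untouched. It is worth correcting because forced entry with a block test holds about 5% per model whichever meaning was intended.

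**What to change.** In C.13.c, replace linear stepwise regression with hierarchical linear regression with forced entry:
- Step 1: total lesion volume.
- Step 2: all Table 1 regions for that process, entered together.
- The F-change for the step 2 block, at a stated significance level, is the test for that process. Visual-proprioceptive integration has two behavioral tests in Table 1, so say that each gets its own model.
- Interpret individual region weights for significance only if the block test is significant, or use multiplicity-adjusted p-values.
- Report every region's weight with a 95% confidence interval, whatever its p-value.

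In C.13.b, change only the name, to hierarchical regression.

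This needs no new data. The price is that individual weights will have wider intervals when damage to the regions is correlated, which reflects how far the data can separate them. The block test controls error within each model, not across the four processes, and it does not alter the region-by-region t-tests.
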